	Incidence rate of atrial fibrillation (AF)
	Tertiary endpoints: 1) Change in functional class (NYHA). 2) Safety
	endpoints (incidence rate of Major hypoglycemia, Symptomatic hypotension,
	Genito-urinary infections, Ketoacidosis, Amputation, and Necrotizing Fasciitis
	of the Perineum (Fournier's Gangrene). 3) Crossovers.
Population	Patients with aortic stenosis and prior history of HF or reduced LVEF
	discharged after TAVI.
Inclusion criteria	• ≥18 years old.
	Severe aortic stenosis underwent TAVI.
	Prior heart failure admission and one of the following criteria:
	➤ Left ventricular ejection fraction ≤ 40% or
	Diabetes mellitus or
	➤ Estimated glomerular filtrate rate 25-75 ml/min/1.73 m2
Exclusion criteria	Known allergy or intolerance to SGLT2 inhibitors.
	Concomitant therapy with sulfonylurea or SGLT2 inhibitors.
	• Systolic blood pressure < 100 mmHg or diastolic blood pressure < 50
	mmHg.
	An estimated glomerular filtration rate (GFR) below 25 ml per
	- , , , -

[figure not shown]

	minute per 1.73 m2.
	_
	Chronic cystitis and/or recurrent urinary tract infections (2 or more in
	the last year)
	Poor control of diabetes mellitus that requires SGLT-2 inhibitor
	prescription on discharge according to treating physician judge.
	Any medical condition that, in the investigator's judgment, would
	seriously limit life expectancy (less than one year).
	Pregnant or breast-feeding patients
	Patients participating in other clinical trials.
Phase	IV.
Number of Sites	26.
Study Drug	Dapagliflozin 10-mg daily dose.
Comparator	Control (no dapagliflozin).
Power calculation	- Anticipated effect size: dapagliflozin treatment will be associated with a 30%
	reduction in the incidence rate of the primary composite endpoint
	Anticipated incidence control arm: 30%
	Anticipated incidence in dapagliflozin arm: 21%
	- Power: 0.8
	- Anticipated incidence of withdrawals/losses in follow-up: 5%
	- Sample size (including withdrawals): 1,020 (510 per treatment arm)
Events	Events will be adjudicated by a blinded committee after reviewing information
adjudication	sent by local investigators
Interim analyses	Two interim analyses will be performed on primary endpoint and secondary
	safety endpoints when 33% and 66% of events have been adjudicated (81 and
	172 events respectively).
Chronogram	2021-2024
	Q1 2021: Start of inclusion
	Q1 2022: Half way with inclusion (510 patients)
	Q1 2023: Anticipated end of inclusion (1,020 patients)
	Q1 2024: End of follow-up

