- General monitoring. All patients will receive the usual follow-up performed at their center for patients after TAVI. Once a potential event is detected either by a

local investigator, a report from the local investigator should be sent to the coordinating center for the evaluation by the adjucation committee.

Specific data: Al investigators will be encouraged to report information about ECG, analytical, and echocardiographic data throughout the first year.

DATA SAFETY MONITORING BOARD (DSMB)

A Data Safety Monitoring Board (DSMB) will be established to formally review the accumulating data from this trial to ensure there is no avoidable increased risk for harm to subjects. Two interim analyses will be performed on primary endpoint and secondary safety endpoints when 33% (81) and 66% (172) of events have been adjudicated (see interim analysis section below). The DSMB will be chaired by an academic cardiologist who is an expert in TAVI care and statistical analyses in clinical trials.

STUDY SCHEDULE

- **SCREENING:** During hospitalization for TAVI.
- ENROLLMENT/BASELINE. At discharge, randomization will take place and baseline patient data will be recorded. The investigator must ensure that the patient signs the informed consent, meets the inclusion criteria and has no exclusion criteria.
- **OPEN-LABEL TREATMENT PHASE:** 2 years.
 - FOLLOW-UP. At 3±1 and 12 months. Clinical follow-up (telephone and medical history revision) will be performed to detect any potential event (end-points and adverse events). To report data about echocardiography and laboratory tests during the first year will be optional
 - o FINAL FOLLOW-UP. 1 year after last patient enrolment. All patients underwent 12 months follow-up.
 - o EARLY TERMINATION VISIT. In case the patient leaves the study ahead of time (due to personal decision), a clinical follow-up (telephone and medical history) will be performed at the time of leaving the study.

	SCREENING	ENROLLMENT	STRATEGY	
	During admission	At discharge	After d Month 3±1	ischarge Month 12
Administrative data				
Inclusion/exclusion criteria	Х			
Informed consent		X		
Demographic		X		
Clinical data				
Medical history		X		
Data about TAVI		X		
Physical examination		X		
Medication history		X		
ECG		X	X*	
Echocardiography		X	X*	
Laboratory data		X	X*	
Medication at discharge		X		
Drug (dapagliflozin yes/no)				
Randomization		X		
Follow-up				
Vital status			X	X
Events of end-point			X	X
Adverse events			X	X

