> Assumptions:

- Overall alpha value: 0.05
 - o Haybittle-Peto approach for interim monitoring
 - 1st interim analysis: alpha value of 0.001
 - 2nd interim analysis: alpha value of 0.001
 - Final analysis: alpha value of 0.05
- Power: 0.80.
- Test: log-rank (superiority two-sided)
- Minimal treatment effect: HR 0.70.
- 1-year incidence of primary endpoint (controls): 30%
- Accrual period: 2 years
- Follow-up period: 1 year for all patients.
- Percentage of subjects anticipated to withdraw: 5%
- Number of expected primary endpoints: 260.
- > Sample size: 1,020 participants

ADAPTIVE SAMPLE SIZE: The sample size for this study was based on the anticipated incidence of the composite endpoint. It is anticipated that the 1-year incidence of the primary endpoint will be 30% in the control arm and 21% in the dapagliflozin arm (thus, 25.5% in the overall population). To reduce the chances of having an underpowered study secondary to an event rate lower than predicted, a blinded examination of the study overall event rate will be done 3 months before closing the recruitment. At that moment, it is anticipated that >400 patients already underwent 12 months follow-up. In the case that the overall event rate is below 25%, the DSMB will discuss the possibility to doing a re-calculation of sample size according to actual event rate, and the chair will decide if it is needed to increase sample size (thus

extend recruitment period). As this analysis will be performed in a blinded fashion, adjustment for multiplicity is not required and will not be applied.

INTERIM ANALYSIS

Two interim analyses will be performed on primary endpoint and secondary safety endpoints when 33% (86) and 66% (172) of events have been adjudicated. Efficacy and safety interim analyses will be performed following the same methodological guidelines described in this document for the final analysis. Stopping rules for efficacy analysis will be based on the statistical Haybittle-Peto approach, with an overall alpha value 0.05. Safety analyses will be addressed by applying descriptive statistical methods to the data, supplemented by calculation of confidence intervals. No formal statistical stopping rules for safety data will be predefined.

REDUCING BIAS

• Randomization:

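### The sample size uses two different effects (HR 0.70, and 30% vs 21%, which is HR 0.66), and the first interim look is set at both 81 and 86 events

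*Combined protocol and SAP*

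**What the plan says.** **Effect.** The Assumptions list under Sample Size gives "Minimal treatment effect: HR 0.70", a 1-year control incidence of 30%, a two-sided log-rank test, power 0.80, overall alpha 0.05, 5% withdrawals, "Number of expected primary endpoints: 260" and 1,020 participants. The Adaptive Sample Size paragraph that follows ties the size to the incidences it anticipates, namely "30% in the control arm and 21% in the dapagliflozin arm (thus, 25.5% in the overall population". The Power calculation row of the synopsis says "Anticipated effect size: dapagliflozin treatment will be associated with a 30" per cent reduction in the incidence rate of the composite. It then lists 30% and 21% beside power 0.8, 5% withdrawals and 1,020 patients, and gives no hazard ratio.

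**Recalculation.** If the blinded overall event rate is below 25%, the DSMB is to discuss a "re-calculation of sample size according to actual event rate". The text does not say which treatment effect stays fixed.

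**Interim looks.** The Interim Analysis section places them "when 33% (86) and 66% (172) of events have been adjudicated". The DSMB section has "secondary safety endpoints when 33% (81) and 66% (172) of events have been adjudicated", and the synopsis has "safety endpoints when 33% and 66% of events have been adjudicated (81 and" 172).

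**The concern.** A hazard ratio and a ratio of 1-year risks are close when events are rare. At a 30% control risk they are not. The 21% equals 0.30 × 0.70, so the hazard ratio appears to have been applied as a risk ratio. Three things depend on it:

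- whether the stated power belongs to the stated incidences;
- what overall event rate the plan expects, and so how close the 25% recalculation threshold lies to expectation;
- what answer a recalculation would give, since the two effects need very different numbers of patients.

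The 81/86 discrepancy matters because the count triggers a formal efficacy look, and the section describing the DSMB's task carries a different count from the statistical section.

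**Working it through.** **Inputs (Sample Size section and synopsis).** Two-sided alpha 0.05 (z = 1.960), power 0.80 (z = 0.842), 1:1 allocation, control 1-year risk 0.30, one year of follow-up per patient, 5% withdrawals. (1.960 + 0.842)² = 7.849.

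**1. Reproducing 1,020 and 260.** Schoenfeld events at HR 0.70: 4 × 7.849 / (ln 0.70)² = 246.8, rounded up to 247. Then 247 / 0.255 = 968.6, rounded up to 969, and 969 / 0.95 = 1,020. Also 1,020 × 0.255 = 260.1. So 1,020 can be reached exactly by taking the events from HR 0.70 and the overall rate from 30% vs 21%. The 260 is then the event count with no allowance for withdrawals.

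**2. Converting each effect (proportional hazards).**
- HR 0.70: treated risk 1 − 0.70^0.70 = 0.221; overall (0.300 + 0.221) / 2 = 0.260.
- 30% vs 21%: HR = ln(0.79) / ln(0.70) = 0.661; overall 0.255.

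**3. Size for power 0.80.** Freedman events are 7.849 × [(1 + HR) / (1 − HR)]². Patients = events / overall rate / 0.95.

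| | HR 0.70 (overall 26.0%) | 30% vs 21% (HR 0.661, overall 25.5%) |
|---|---|---|
| Schoenfeld events; patients | 246.8; 997 | 183.0; 756 |
| Freedman events; patients | 252.0; 1,019 | 188.3; 777 |
| Two proportions, per arm; total with 5% withdrawals | 483; 1,017 | 367; 773 |

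**4. Power with 1,020 patients.** Power = Φ(√events × |ln HR| / 2 − 1.960) by Schoenfeld; Freedman replaces |ln HR| / 2 by (1 − HR) / (1 + HR). The range of events runs from full loss of the 5% to no loss.
- HR 0.70, 252 to 266 events: 0.809 to 0.828 (Schoenfeld), 0.801 to 0.820 (Freedman).
- 30% vs 21%, 247 to 260 events: 0.902 to 0.916 (Schoenfeld), 0.894 to 0.909 (Freedman).
- Two proportions fall in the same bands: 0.80 to 0.82, and 0.90 to 0.91.

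**5. Expected events in 1,020 patients at HR 0.70.** With no withdrawals, 1,020 × 0.2605 = 265.7. If the 5% contribute nothing, 265.7 × 0.95 = 252.4. If withdrawals are spread over the year, each arm gives 510 × λ/(λ + δ) × (1 − e^−(λ+δ)), where λ = −ln(1 − risk) and δ = −ln 0.95; the two arms total 259.3.

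**6. Recalculation at assumed overall rates.** For a risk ratio of 0.70, the control risk is 2 × overall rate / 1.70. At 24% that gives 28.2% vs 19.8%, HR 0.664.

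| Assumed overall rate | HR 0.70 held | Risk ratio 0.70 held |
|---|---|---|
| 24% | 1,082 to 1,105 | 820 to 843 |
| 22% | 1,181 to 1,206 | 918 to 944 |

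(Schoenfeld to Freedman.) The first column exceeds 1,020 and the second does not.

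**7. Interim counts.** 33% and 66% of 260 are 85.8 and 171.6, that is 86 and 172. By contrast 81 / 0.33 = 245 and 172 / 0.66 = 261, so no single total gives both 81 and 172; 81 is 31% of 260. The observed HR needed for p < 0.001 is exp(−2 × 3.2905 / √events): 0.48 at 81 events and 0.49 at 86.

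**8. Alpha (minor).** Levels 0.001, 0.001 and 0.05 at 86, 172 and 260 events give an overall two-sided alpha of 0.0505 by multivariate normal integration. With 0.0495 at the final analysis it is 0.0500.

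**The case against.** The best defence is that 0.70 is labelled a minimal effect while 30% vs 21% is labelled anticipated. A trial may be powered at 0.80 for the smallest effect of interest and still expect a larger one. That reading does not survive the text: the Adaptive Sample Size paragraph bases the size on the anticipated incidences, and the synopsis sets 21% directly beside power 0.8.

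A second defence is that the synopsis speaks of a 30% reduction in the incidence rate, which as a rate is HR 0.70. That moves the inconsistency inside the synopsis, because the 21% listed under it is a 30% reduction in risk.

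On the recalculation, holding the listed HR and updating the event rate is arguably the natural reading, and the DSMB's role is discretionary. That is fair, but the plan does not say so, and the paragraph holding the rule cites only the incidences.

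Some of the case stands. The practical impact is modest. The value 81 has a plausible origin, since 33% of 247 required events is 81.5, but 66% of 247 is 163, not 172. A continuity-corrected two-proportion test gives 819 patients for 30% vs 21%, above the range quoted here but still far from 1,020. The alpha excess is immaterial.

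**Conclusion.** The concern holds. The plan states two effects and attaches to both a power that fits only HR 0.70: 80% to 83% with 1,020 patients, against 89% to 92% for 30% vs 21%. Planned enrolment is adequate under either effect. What is wrong is the set of figures: the treated-arm and overall incidences or the hazard ratio, the power, an event total that ignores withdrawals, and the effect left unspecified for the recalculation. The first interim trigger is a plain contradiction of small consequence.

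The conversion between hazard ratio and risk assumes proportional hazards, which the planned Cox model also assumes, and one year of follow-up. The recalculation figures rest on assumed overall rates of 24% and 22%. With the continuity-corrected test the patient numbers shift, but the conclusion does not.

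**What to change.** 1. Use one effect in the synopsis and the Sample Size section. Either keep HR 0.70 and power 0.80 and replace 21% by 22.1% and 25.5% by 26.0%, or keep 30% vs 21% and state HR 0.66 with about 90% power for 1,020 patients.
2. Name the formula and restate the derivation, since 25.5% is the input that gives exactly 1,020. At HR 0.70 throughout, Freedman gives 1,019 and Schoenfeld 997.
3. State the expected events with the withdrawal assumption. For HR 0.70 this is 259 if withdrawals are spread over the year.
4. State in the Adaptive Sample Size paragraph which effect is held fixed in the recalculation.
5. While 260 remains the total, change 81 to 86 in the synopsis and the DSMB section. If the total changes, recompute both looks: 33% and 66% of 259 are 85.5 and 170.9.
6. Optional: give the overall alpha as about 0.0505, or test at about 0.0495 at the final analysis.

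These are text corrections with no change in planned enrolment. The optional step would lower the final significance level by 0.0005.

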- 6. **Flexibility (adherence)** how different is the flexibility in how participants must adhere to the intervention and the flexibility likely in usual care?
 - Patients receive usual encouragement to adhere to the intervention.
 Medical care providers are encouraged to maintain treatment unless a new clear clinical indication is present. No other measures to improve compliance. (Score 4)
- 7. **Follow-up** how different is the intensity of measurement and follow-up of participants in the trial and the likely follow-up in usual care?
 - Participants are followed as usual care except for 3 additional phone contacts during the follow-up period. (Score 4)

- 8. **Primary outcome** to what extent is the trial's primary outcome relevant to participants?
 - The primary outcome is a composite of hard clinically meaningful endpoints: mortality or HF admission. (Score 5)
- 9. **Primary analysis** to what extent are all data included in the analysis of the primary outcome?
 - Primary analysis is performed applying the intention-to-treat principle in the full dataset, no matter whether compliance. (Score 5)

DATA ANALYSIS SET

> Full Analysis Set:

In this document, the term full analysis set is used to describe the analysis set which is as complete as possible and as close as possible to the intention-to-treat ideal of including all randomized subjects. Participants who fail to satisfy an entry criterion (eligibility violations) will be excluded from this dataset. In order not to introduce bias, the following circumstances have to apply:

- The entry criterion will be measured prior to randomization.
- The detection of the relevant eligibility violations will be made completely objectively.
- o All detected violations of the particular entry criterion will be excluded.

> Per Protocol Set:

The per protocol set is the subset of the subjects in the full analysis set without treatment crossovers. In this data set, participants who switch from their randomized treatment will be therefore censored at the time of their switch.

RANDOMIZATION

Randomization will be performed centrally via a web or dedicated mobile application. Randomization will follow a permuted-block design with varying block sizes to ensure the continued equivalence of each group size and will be estratified according to center.

STATISTICAL PLAN: SAMPLE SIZE CALCULATION, ADAPTIVE DESIGN, INTERIM ANALYSES

SAMPLE SIZE

The number of subjects was determined for the primary endpoint of the trial.

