Randomization introduces a deliberate element of chance into the assignment of treatments to subjects in a clinical trial. In this trial, randomization procedure is organized centrally, and it is characterized by being stratified by center and follows a permuted-block design with varying block sizes to reduce predictability of the random sequence.

Blinding:

As this trial follows a PROBE design, open-label and blinded endpoint adjudication are intrinsic characteristics. Masking is no implemented for patient and care provider. Therefore, to reduce potential bias, the endpoint adjudication panel remains blinded to treatment allocation and hard clinical meaningful endpoints have been selected as primary endpoint.

• Multiplicity:

Multiplicity can raise concerns regarding type I error. To address multiplicity problems, two strategies are implemented. First, a composite endpoint is selected as primary endpoint. Second, Haybittle-Peto approach is applied to account for interim analyses.

• External validity:

The pragmatic design of this trial, as evaluated through PRECIS-2 guidelines, increases the generalizability of its conclusions to real daily clinical practice.

DESCRIPTIVE ANALYSIS

The distribution of continuous variables will be analyzed with graphical methods. For normally distributed variables, results will be expressed as mean \pm SD; otherwise they will be represented as median (first quartile to third quartile). Categorical variables will be expressed as absolute frequency (%). Significance testing of baseline differences between treatment groups will be not performed.

PRIMARY ANALYSIS

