Primary analyses will be performed in the "full data set" in an intention-to-treat fashion. The intervention arm will be compared against the control arm for the composite primary endpoint. Time-to-event will be evaluated using the Kaplan-Meier survival analysis followed by multivariable Cox proportional hazards model. Hazard ratios (HR) with corresponding 95% confidence intervals will be calculated for treatment effect estimation. All patients without an event will be censored at last day of follow-up. Patients that withdraw from follow-up will be considered censored on the day of withdrawal. Due to the randomization process and the large sample size of the trial, it will be not expected the presence of covariate relevant imbalances between treatment groups. However, for exploratory purpose, standardized differences will be calculated. Those known prognostic factor presenting an imbalance higher than 0.1 standardized difference will be included in the multivariable Cox model. For all tests, we will use 2-sided p-values with alpha ≤0.05 level of significance.

SECONDARY ANALYSIS

The secondary endpoints will be the individual components of the primary composite endpoint, besides CV mortality and the development of new atrial fibrillation. Analyses will be performed following the same guidelines described for primary analysis. Multiplicity adjustment will be not implemented because the hierarchical structure between primary and secondary endponits.

To better explore the treatment effect under ideal circumstances (explanatory approach), primary and secondary endpoint analyses will be replicated in the "per protocol data set" using same methods described above.

SUBGROUP ANALYSIS

All subgroup analyses will be performed using interaction models based on the primary analysis model, also including the subgroup in question and the treatment-subgroup interaction as factors, and presented as treatment hazard ratios for each subgroup and the interaction p-value. Subgroups will be specified in the endpoints section below.

PRE-SPECIFIED SUB-GROUP ANALYSES

- > Diabetic vs non-diabetic patients.
- ightharpoonup LVEF < vs > 40%.
- \geq 80 years vs < 80 years of age on recruitment
- ➤ Males vs females
- ➤ Atrial fibrillation versus sinus rhythm
- > Hypertensive vs normotensive patients
- ➤ Moderate-severe vs mild LVH.
- > Treatment with beta-blockers vs. no beta-blockers

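### Randomisation is stratified by centre but the primary analysis does not use centre: the test is slightly conservative and loses modest power if centre risks differ widely

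*Combined protocol and SAP*

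**What the plan says.** The Randomization section says that allocation uses permuted blocks of varying size and "will be estratified according to center". The Reducing Bias section repeats this: "it is characterized by being stratified by center". The synopsis gives 26 sites.

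The sample-size assumptions list "Test: log-rank (superiority two-sided") with no strata. The Primary Analysis section says "Time-to-event will be evaluated using the Kaplan-Meier survival analysis followed by multivariable Cox proportional hazards model". It names no test, and no centre stratum, covariate or random effect. Covariates enter the Cox model only if they are known prognostic factors whose standardised difference between arms exceeds 0.1.

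The interim analyses and the secondary endpoints follow the same methods, and the subgroup models are built on the primary model, so the omission carries over to them.

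**The concern.** Blocking within centre removes between-centre variation from the treatment comparison. An analysis without centre still counts that variation in its standard error, so it does not match the way patients were allocated.

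The imbalance rule does not repair this, because blocking is designed to keep centre balanced.

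Centre differences are plausible here. Telephone follow-up may be local or run by the coordinating centre, hospitals with electronic records are preferred but not required, and local investigators identify potential events. The endpoint also includes urgent visits with intravenous treatment, which may depend on local practice. At stake is some of the efficiency that stratified randomisation makes available.

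**Working it through.** **1. The plan's own figure.** Inputs from the sample-size section: two-sided alpha 0.05, power 0.80, hazard ratio (HR) 0.70, overall 1-year incidence 25.5%, withdrawal 5%.
- Events = 4(1.960 + 0.842)² / (ln 0.70)² = 246.8, so 247.
- Patients = 247 / 0.255 = 968.6, so 969; 969 / 0.95 = 1,020.

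This matches the stated 1,020. The stated 260 events are 1,020 × 0.255, with no withdrawals deducted. The sample size is not at fault.

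**2. Would the imbalance rule admit centre?** An average centre has 1,020 / 26 ≈ 39 patients. Block sizes are not given. If the largest is 6, the arms within a centre differ by at most 3, for example 21 against 18. As shares of 510 per arm these are 4.12% and 3.53%. The standardised difference is 0.0059 / 0.192 ≈ 0.03, well under 0.1.

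**3. What the mismatch costs.** The between-centre SD of the log hazard is an assumption. To show what it means, the 10th to 90th centile centre has control risk 1 − exp(−λ·exp(±1.2816·SD)), with λ set so that the mean control risk is 30%:
- SD 0.3 (λ = 0.347): about 21% to 40%
- SD 0.5 (λ = 0.331): about 16% to 47%
- SD 0.7 (λ = 0.310): about 12% to 53%

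Simulated trials had 1,020 patients, 26 centres, 12 months of follow-up, exponential event times, 5% withdrawal, a log-normal centre effect and permuted blocks within centre. Each cell shows unstratified / centre-stratified. Type I error is at HR 1; power and mean HR are at a within-centre HR of 0.70.

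| SD | Trials per cell, centre sizes | Type I error % | Power % | Mean HR |
|---|---|---|---|---|
| 0 | 10,000, unequal | not listed | 81.1 / 80.8 | not listed |
| 0 | 6,000, equal | 5.0 / 5.1 | 81.9 / 81.6 | 0.698 / 0.698 |
| 0.2 | 6,000, equal | 4.8 / 5.1 | 81.6 / 81.5 | 0.701 / 0.700 |
| 0.4 | 6,000, equal | 4.8 / 5.3 | 80.6 / 82.0 | 0.704 / 0.698 |
| 0.5 | 10,000, unequal | 4.3 / 5.1 | 78.8 / 80.6 | 0.71 / 0.70 |
| 0.6 | 6,000, equal | 4.3 / 5.2 | 77.6 / 80.7 | 0.714 / 0.701 |
| 0.7 | 10,000, unequal | 3.8 / 4.6 | 77.2 / 81.4 | 0.72 / 0.70 |
| 0.8 | 6,000, equal | 3.4 / 5.2 | 75.2 / 81.6 | 0.722 / 0.699 |

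At SD 0.3 the 10,000-trial run showed no material difference. A further 3,000-trial run gave power of 80.2 / 82.2 at SD 0.5 and 77.8 / 81.8 at SD 0.7. The 6,000-trial runs repeated with unequal centres show the same pattern, with a loss of about 5 points at SD 0.8. Monte Carlo error on a single power figure is about 0.4 to 0.7 points, depending on the run.

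**4. Where the power goes.** Take SD 0.6, HR 0.70, equal centres.
- Unstratified: mean model SE 0.1258, actual SD of the log HR 0.1210, ratio 1.04. Mean Z = 0.3376 / 0.1258 = 2.68. Power ≈ Φ((2.68 − 1.96) / 0.962) ≈ 77%.
- Stratified: SE 0.1263, actual SD 0.1260, ratio 1.00. Mean Z = 0.3555 / 0.1263 = 2.81. Power ≈ Φ((2.81 − 1.96) / 0.998) ≈ 80%.

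The two model SEs are practically equal. The gain comes from the estimate not being pulled in and from correct calibration, not from a narrower interval.

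**The case against.** Five points can be made on the other side.

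- **The interval.** A reader might infer that stratifying would narrow the confidence interval. It would not: the SEs are 0.1258 and 0.1263 in the example above. The planned interval is too wide only relative to the estimator's actual variability under blocking. This stands, and the point is confined to calibration.
- **The hazard ratio.** A reader might infer that the planned estimate is biased. The unstratified model estimates a marginal HR and the stratified model a within-centre HR. These differ even with perfect balance, and a marginal effect is defensible in a pragmatic trial. This stands as well. What remains is that the plan does not say which it wants.
- **The size.** The loss rests on an SD that the documents do not give. All centres share one set of entry criteria and blinded central adjudication, which may limit the spread. Nothing in the documents establishes centre control risks as far apart as 12% and 53%. This stands: the direction is firm, the size is not.
- **The direction of the error.** Type I error falls below 5%, so a positive result would not be undermined. This stands.
- **The test.** The log-rank test appears only among the sample-size assumptions, and the Primary Analysis section names no test. So part of the fault is silence rather than a deliberate unstratified choice. The remedy is the same.

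**Conclusion.** The mismatch is real, and its consequence is modest and conditional. If centre risks differ substantially, the planned analysis is slightly conservative, reports an HR of about 0.71 to 0.72 where the within-centre value is 0.70, and gives up about 2 points of power at an assumed SD of 0.5 and about 4 points at 0.7. At SD 0.3 or below the loss is negligible.

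A reader might go further and conclude that the trial is underpowered by design or that its primary result would be invalid. The documents support neither: the 1,020 reproduces at 80% power, and the error runs against the treatment rather than for it. The change is worth making because it costs almost nothing. These results assume exponential event times, a log-normal centre effect, and block and centre sizes that the plan does not give.

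**What to change.** - **Sample-size assumptions:** write *two-sided log-rank test stratified by centre*.
- **Primary Analysis:** name that as the primary test, take the HR and 95% confidence interval from a Cox model stratified by centre, and state that the target is the within-centre HR.
- **Small centres:** fix a rule for pooling very small centres (for example, those with fewer than 10 randomised patients) before any outcome by arm is seen.
- **Other analyses:** the same strata can serve the secondary time-to-event endpoints and the interim looks.

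**Cost.** A few sentences. Centre is already known from the investigator's log-in, so no new data or patients are needed. If centres do not differ, stratifying costs about 0.3 points of power. That figure was checked only for the final primary analysis, and without pooling.

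The cost is somewhat larger at the first interim look, where 86 events over 26 centres is about 3 per centre. The stratified SE there is up to about 3% larger. With even recruitment over two years and unequal centres it is nearer 1.5% (0.2233 against 0.2201 with no centre differences). The choice should be fixed before unblinded results are seen.
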